5.2.6 Electrocardiogram

5.2.6.1 ECG Recording – Phase Ib and Phase II

Triplicate 12-lead ECGs (each ECG to be taken approximately 2-3 minutes apart) will be performed in all patients at the time-points as specified in the Flow Chart and Appendix 10.6 and will be coincident to PK sampling. The investigator will review the ECG recording, comment on any clinical significance and if applicable record any ECG abnormality that meets AE criteria.

Triplicate ECGs will be recorded at the following time-points:

- Screening
- Pre-dose (-20 min. to -5 min. before administration of BI 836845 and/or enzalutamide) and immediately after the end of infusion of BI 836845 (within 15 minutes after the end infusion to ensure PK sampling is also completed within 15 minutes), or one hour after the administration of enzalutamide on the following days*:
 - o **Cycle 1:** Day 1, Day 8, Day 15
 - o **Cycle 2:** Day 8, Day 15
 - o **Cycle 3:** Day 1, Day 8, Day 15
 - O Cycles 6, 9, 12 and in 12 weeks intervals thereafter on Day 1
- EOT
- First follow-up visit only
- * ECGs to be taken prior to PK sample time-points where applicable. See appendix 10.6 for ECG flowchart.

ECGs will only be correlated to PK for the drug combination (BI 836845 and enzalutamide) during phase Ib and phase II arm A.

All ECGs will be recorded digitally with ECG equipment provided by a CRO ECG core lab.

Before study start the study sites will be trained for the proper use of the equipment and transfer of the electronic data to the CRO core lab. To be able to assess the electrocardiographic variables in resting phases the ECGs have to be recorded in supine position after the subjects were at rest for at least ten minutes. At specific time-points triplicate ECGs will be recorded to minimize the physiologically induced QT and heart rate variability. The recordings will be evaluated at the site by the investigator (or delegate) to assess any ECG abnormalities and changes in interval duration. ECG abnormalities will be

Doc. No.: c02304008-15 Page 73 of 241 Proprietary confidential information. © 2022 Boehringer Ingelheim International GmbH or one or more of its affiliated companies. All rights reserved.

carefully monitored and, if necessary, the subject will be removed from the trial and medically treated.

All ECGs will be sent to the CRO core lab to centrally and independently evaluate the electrocardiograms.

After the primary analysis of the study, a decision can be made by the sponsor and communicated by the trial clinical monitor to stop the centralized ECG review if necessary. Thereafter the ECG will be evaluated locally by the investigator if clinically indicated

5.2.6.2 ECG evaluation

The digitally recorded ECGs sent to the CRO core lab will be evaluated for cardiac intervals (RR, PR/PQ, QRS, QT and heart rate-corrected QT (QTc)). Measurements of the cardiac intervals will be done from three (possibly consecutive) normal heart complexes in lead II using the core lab's procedures. Heart rate correction of QT intervals will be done using Fridericia's and Bazett's formula. In addition, the ECGs will be reviewed by a board-certified cardiologist using a standardized worksheet to obtain clinically significant findings such as rhythm, morphology, and conduction abnormalities as well as those of ST Segments, T and U waves. The central measurement of the ECG intervals will be done in all ECGs. In triplicate ECG recordings one randomly selected ECG from this time-point will be evaluated. In case of clinically significant abnormalities (e.g. heart blocks or large changes in interval duration) the CRO core lab may contact the investigator and vice versa. Changes in OT interval compared to baseline will be evaluated internally at BI.

5.2.7 Left ventricular ejection fraction

Left Ventricular Ejection Fraction (LVEF) as measured by echocardiography or MUGA scan will be assessed at screening and post treatment if clinically indicated. The same method of measurement should be used throughout the study.

5.2.8 Assessment of vital signs and physical examination

Vital signs (blood pressure, pulse and respiration rate after two minutes supine rest) and temperature will be recorded at the screening visit and at the time points specified in the Flow Chart.

A physical examination, including weight, will be performed at screening and at the time points specified in the Flow Chart. The physical examination should include a thorough cardiopulmonary examination, an examination of the regional lymph nodes, an examination of the abdomen and an assessment of the mental and neurological status. Additional symptoms which have not been reported during a previous examination should be clarified. A physician should perform this examination. Measurement of height (in cm) and body weight (in kg) and the evaluation of the ECOG performance score and will be performed at the time points specified in the Flow Chart.

5.2.9 **Demographics and medical history**

Demographics (sex, birth date and race) and baseline conditions will be collected during the screening visit.

Trial Protocol Version 12

Page 74 of 241

Proprietary confidential information. © 2022 Boehringer Ingelheim International GmbH or one or more of its affiliated companies. All rights reserved.

Cancer history will also be obtained.

- The month/year of first biochemical/histological/cytological diagnosis of prostate cancer.
- Age at diagnosis
- Gleason score at the time of diagnosis (if known).
- Site of metastasis, e.g. visceral (specify such as liver or lung), bone, lymph nodes
- Type of progression at study entry, i.e. PSA, radiological and/or symptomatic
- Confirmation on whether documented information on relapse or progressive disease is present at screening.
- Previous surgeries and dates of surgeries will be reported (if known).
- Number and type of previously administered chemo-, immuno-, hormone-, molecular targeted and biological therapies, including radiotherapy, will be reported, only if known, including specification of the treatment protocol/name of treatment for prostate cancer. All treatment start and stop dates will be recorded.
- The best response obtained to these treatments should also be recorded if information is available (Complete Response, Partial Response, Stable Disease, Progressive Disease, or unknown).

06 Jun 2022

Doc. No.: c02304008-15 Trial Protocol Version 12 Page 75 of 241

5.4 APPROPRIATENESS OF MEASUREMENTS

The RECIST criteria version 1.1 (R09-0262 and appendix 10.4) to be used for evaluation of tumour response are well established and scientifically accepted. The Common Terminology Criteria, CTCAE version 4.03, 14 June 2010 (R10-4848 and 5.1.2.1) are used in the assessment of adverse events in cancer patients.

All measurements performed during this trial will be to monitor safety and tolerability of BI 836845 in combination with enzalutamide, to determine the MTD and /or recommended phase II dose during the phase Ib tolerability and safety phase, and to collect further safety data during the randomised phase II phase of the trial.

The scheduled assessments are to monitor drug induced changes in respect to vital signs, standard laboratory values and ECG. Tumour evaluations are necessary for determination of tumour response to treatment

PSA

Page 78 of 241

measurements will be used to confirm changes from baseline during treatment and to confirm PSA response and progression.

Doc. No.: c02304008-15

Page 79 of 241

 $Proprietary\ confidential\ information. ©\ 2022\ Boehringer\ Ingelheim\ International\ GmbH\ or\ one\ or\ more\ of\ its\ affiliated\ companies.\ All\ rights\ reserved.$

Doc. No.: c02304008-15

Trial Protocol Version 12

Page 80 of 241

 $Proprietary\ confidential\ information. @\ 2022\ Boehringer\ Ingelheim\ International\ GmbH\ or\ one\ or\ more\ of\ its\ affiliated\ companies.\ All\ rights\ reserved.$

Doc. No.: c02304008-15

Trial Protocol Version 12

Page 81 of 241

06 Jun 2022

 $Proprietary\ confidential\ information. ©\ 2022\ Boehringer\ Ingelheim\ International\ GmbH\ or\ one\ or\ more\ of\ its\ affiliated\ companies.\ All\ rights\ reserved.$

06 Jun 2022

Doc. No.: c02304008-15 Trial Protocol Version 12 Page 82 of 241

Doc. No.: c02304008-15

Trial Protocol Version 12

Page 83 of 241

 $Proprietary\ confidential\ information. @\ 2022\ Boehringer\ Ingelheim\ International\ GmbH\ or\ one\ or\ more\ of\ its\ affiliated\ companies.\ All\ rights\ reserved.$

Boehringer Ingelheim BI Trial No.: 1280.8 Doc. No.: c02304008-15 06 Jun 2022

Trial Protocol Version 12

Page 84 of 241

 $Proprietary\ confidential\ information. @\ 2022\ Boehringer\ Ingelheim\ International\ GmbH\ or\ one\ or\ more\ of\ its\ affiliated\ companies.\ All\ rights\ reserved.$

Doc. No.: c02304008-15 Trial Protocol Version 12 Page 85 of 241

6. INVESTIGATIONAL PLAN

6.1 VISIT SCHEDULE

6.1.1 Screening Visit: -28 to day -1

All screening assessments will be performed within 28 days of first administration of study drug/s on day 1 (visit 1) of cycle 1. Patients who have signed the informed consent and meet all eligibility criteria will be scheduled to begin treatment with either: BI 836845 and enzalutamide (phase Ib and phase II arm A), or enzalutamide alone (phase II arm B).

6.1.2 Treatment Visits

The treatment phase of the study will start on the first day of infusion of BI 836845 in cycle 1. Administration of BI 836845 will be weekly and enzalutamide will be daily over a 28 day cycle of treatment in phase Ib and phase II of the study.

All treatment cycles will comprise of four visit days as per the Flow Chart Phase Ib and Phase II.

During the phase II randomised trial of the study from cycle 4 onwards patients on arm B (enzalutamide only) will only be required to attend for one visit per cycle on day 1 and when imaging assessments are scheduled; optional telephone contact calls may be included at day 8, day 15 and day 22 per cycle where required, and at the discretion of the investigator, for the collection of AE and concomitant medication information. For those patients receiving the combination treatment in any part of the trial, and who later discontinue BI 836845 permanently, they may attend only on day 1 of every cycle, from cycle 4 onwards, and when imaging assessments are scheduled.

For those patients that complete cycle 3 in phase Ib and phase II, these cycles will be repeated where clinical benefit is indicated. All assessments stated for cycle 3 in phase Ib and phase II will be repeated for all subsequent cycles, unless otherwise indicated in the Flow Chart.

Tumour assessments, including bone scans, will be performed as per the Flow Chart at week 8, week 16, week 24, week 36 and every 12 weeks thereafter. All tumour assessment visits may be within 7 days prior to the start of the respective cycle of treatment.

PK, biomarker assessments, PSA, CTC and immunogenicity sampling will be conducted for all days stated in the Flow Chart and Appendix 10.6.

No visit windows will be permitted on day 1 (visit 1) at the start of a cycle. On days 8, day 15 and 22 of every cycle a ± 1 day window will be permitted.

All planned visit dates are programmed from the start of day 1 (visit 1) of cycle 1. If a visit is missed there will be no re-scheduling; if a patient should attend the study site between the "missed" and scheduled visit, then the missed visit assessments should be performed. The current date and the reason for the delay must be noted in the medical records. All subsequent visits must adhere to the scheduled programme of visits for all cycles of treatment.

In situations where a patient is unable or unwilling to attend a clinic visit, the investigator must assess the risk-benefit balance for the individual patient and may decide to perform a

Page 86 of 241

BI Trial No.: 1280.8 Doc. No.: c02304008-15

Proprietary confidential information. © 2022 Boehringer Ingelheim International GmbH or one or more of its affiliated companies. All rights reserved.

visit remotely if this is in the best interests of the patient and if agreed with the sponsor, provided that it is allowed by local country regulations and the investigator ensures that the local facilities are adequately qualified to perform the tests required per protocol for the given visit.

[figure not shown]
The following assessment can be done remotely: assessment of ongoing and/ or new adverse events and concomitant medications and compliance check for enzalutamide.

All COVID-19 related deviations from the original schedule of visits and procedures will be documented and the implications considered for the analysis of the trial data.

The treatment phase of the study will continue for an indeterminate number of cycles until one of the criteria for patient removal applies and the end of treatment (EOT), plus the first follow-up visit has been performed.

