All patients should have a tumour assessment/bone scan at EOT visit regardless of the reason for discontinuation, unless the last evaluation was performed within 4 weeks of EOT.

Page 11 of 241

Proprietary confidential information. © 2022 Boehringer Ingelheim International GmbH or one or more of its affiliated companies. All rights reserved.

FLOW CHART – PHASE II RANDOMISED TRIAL (FOR ALL PATIENTS UNTIL APPROVAL OF PROTOCOL VERSION 10)

Study period	Screening						Treat	ment 1						EOT ²	FU ³	OP ⁴
			Сус	ele 1			Сус	cle 2		(Cycle 3/4	4 onwar	ds			
Visits (V)*		V1	V2	V3	V4	V1	V2	V3	V4	V1	V2	V3	V4	EOT	FU	OP
Days (D)	-28 to -1	D1	D8 ±1	D15 ±1	D22 ±1	D1 ±1	D8 ±1	D15 ±1	D22 ±1	D1 ±1	D8 ±1	D15 ±1	D22 ±1		EOT +42 (+7)	
Informed consent ⁵	X															
Demographics	X															
Medical history	X															
Inclusion/exclusion criteria	X	X														
Randomisation ²⁷		X														
Physical exam ⁸	X	X				X				X				X	X ²²	
Height	X															
Body weight	X	X				X				X				X	X	
Vital signs ⁹	X	X	X	X	X	X	X	X	X	X	X	X	X	X	X	
ECG 12-lead - triplicate 10	X	X	X	X			X	X		X	X	X		X	X	
ECHO or MUGA (LVEF)	X															
ECOG performance status	X	X				X				X				X	X	
Safety lab ¹²	X^{13}	X^{13}	X	X	X	X^{13}	X	X	X	X^{13}	X	X	X	X^{13}	X	
Circulating tumour cells (CTC) ¹⁶		X				X				X^{16}				X		
PSA blood sampling ¹⁷	X	X								X^{17}				X		
Tumour assessment / bone scans ²⁰	X									X^{20}				X^{21}		
Adverse event	X	X	X	X	X	X	X	X	X	X	X	X	X	X	X^{23}	
Concomitant therapy	X	X	X	X	X	X	X	X	X	X	X	X	X	X	X	
Arm A & B: Dispense enzalutamide ²⁴		X	X	X	X	X	X	X	X	X	X	X	X			
Arm A & B Drug administration: Enzalutamide						Once o	daily con	ntinuous	dosing							
Arm A Drug administration: Infusion BI 836845		X	X	X	X	X	X	X	X	X	X	X	X			
Compliance check of enzalutamide			X	X	X	X	X	X	X	X				X		1

Boehringer Ingelheim
BI Trial No.: 1280.8

Doc. No.: c02304008-15 Trial Protocol Version 12 Page 12 of 241

Proprietary confidential information. © 2022 Boehringer Ingelheim International GmbH or one or more of its affiliated companies. All rights reserved.

Т	ermination of trial medication							X		
P	atient status								X	X
P	atient completion ²⁵								X	X

- * From cycle 4 onwards patients on enzalutamide (Arm B) and those patients that have discontinued BI 836845, but remain on enzalutamide (Arm A), will only be required to visit on day 1 of each cycle.
- 1. Treatment cycles: each treatment cycle consists of 28 days

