4.1.4.2 BI 836845 (Phase Ib and Phase II - Arm A)

BI 836845 will be given intravenously as a single dose over approximately one hour (60 minutes), with repeated weekly administration on day 1, 8, 15 and 22 of every 28 day cycle of treatment in phase Ib and Arm A in phase II.

BI 836845 will be administered in the exploratory expansion cohort and phase II Arm A, at the MTD and/or recommended phase II dose (RP2D) level determined during phase Ib tolerability and safety (escalation).

Infusion reactions that might occur during infusion with BI 836845, e.g. pyrexia, chills, rigors, dyspnoea, urticaria, bronchospasm, hypotension, hypertension, may be managed by reducing the infusion rate and administering prophylactic antihistamines for subsequent dosing. Severe reactions may require immediate and permanent discontinuation of infusion. A one hour observation period is recommended following each infusion for the first 3 cycles of treatment and at least a 15 minute observation period is recommended following subsequent infusions. See section 4.2.1.1.

Infusion reactions will not be reported on the standard AE page but will be reported on a separate page specifically for infusion reactions in the CRF.

BI 836845 vials will be allocated by the IRT system at every weekly visit.

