6.2.2 Treatment period

The first dose will be on day 1 of cycle 1 and will be considered the start of the treatment period. The starting dose in phase Ib (escalation) of the study will be determined from the dose escalation regimen; for patients entering phase Ib (expansion cohort) and phase II of the study the MTD, or recommended phase II dose, will be the starting dose. Patients in phase Ib will be assigned to cohorts as per instruction from the BI clinical monitor and in consultation with the investigator and site.

06 Jun 2022

Page 90 of 241

Trial Protocol Version 12 $Proprietary\ confidential\ information. @\ 2022\ Boehringer\ Ingelheim\ International\ GmbH\ or\ one\ or\ more\ of\ its\ affiliated\ companies.\ All\ rights\ reserved.$

Safety assessments (safety laboratory tests and vital signs) must be performed prior to dosing on the infusion days in both phase Ib and phase II.

Inclusion and exclusion	Re-check criteria before dosing at C1D1, as per
	section 3.3.2 and 3.3.3.
Randomisation – Phase II only	Randomisation in IXRS.: Randomization may take place up to 3 days prior to the C1D1 if site procedures require advance randomization to accommodate the logistics of dispensing study medication to patients. Sites that use this option must include a copy of site policy/written justification in the ISF and submit a copy to the sponsor. If randomization is performed prior to C1D1, the subsequent visits must be scheduled with reference to C1D1.
Physical examination and body weight	Performed according to Flow Chart - see section 5.2.8.
Vital signs	Performed according to Flow Chart. See section 5.2.8.
	For Phase II Arm B enzalutamide only – vitals performed weekly as per the Flow Chart; however from C4 onwards only at the start of every cycle of treatment on Day 1 until approval of protocol version 10. After approval of protocol version 10 should be done according to standard of care.
ECG – 12 lead (triplicate)	For C1, ECGs to be taken pre-infusion/enzalutamide, and immediately after the end of infusion or one hour after enzalutamide intake at D1, D8 and D15 of the cycle.
	For C2 only ECGs at D8 and D15 of the cycle – preand post-dosing (as described above).
	For C3 ECGs will be performed as described in C1 for on D1, D8 and D15.

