7.3 PLANNED ANALYSES

During phase Ib (escalation), cohorts of patients treated with BI 836845 in combination with enzalutamide will be evaluated continuously based on the safety profile in order to determine the MTD and /or recommended phase II dose. This MTD, and /or recommended phase II dose will be used in the phase Ib expansion cohort and in phase II.

Efficacy analyses will include all randomised patients in phase II. For phase Ib expansion cohort PFS will be summarised on cohort level. No comparisons between dose cohorts will be performed for phase Ib escalation.

Safety analyses will be summarized separately for patients treated in phase Ib and phase II. The safety profile for the phase II patients will be compared in a descriptive manner between the BI 836845 in combination with enzalutamide arm, and the enzalutamide only arm.

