7.8.2 Laboratory data

7.8.2.1 Laboratory data

The analyses of laboratory data will be descriptive in nature and will be based on BI standards (6). The same on-treatment periods as considered for the analysis of AEs will be applied for laboratory values except for that the baseline laboratory value will be included in the 'on-treatment' period. Patients having at least one post-baseline laboratory value will be displayed in the descriptive analyses.

Descriptive statistics, including change from baseline and frequency of patients with transitions relative to the reference range, will be provided. CTCAE grades for applicable laboratory parameters will be calculated according to CTCAE version 4.03 (R10-4848). The following outputs will be presented:

• Worst CTCAE grade experienced during the on-treatment phase.

• Transitions of CTCAE grade from baseline to worst laboratory value, from worst to last laboratory value during the on-treatment phase, and from baseline to last laboratory value.

Patients with missing CTCAE grade at baseline or no baseline value but post baseline values will be displayed in the category "Missing CTCAE grade at baseline". Laboratory values without CTCAE grading will be compared to their reference ranges and frequency tables will be provided for the number of patients within and outside the reference range at baseline and the last measurement on treatment.

Analysis of potentially clinically significant abnormal laboratory values, and handling of CTCAE grade -1 and -9 laboratory parameters, are described in the SOP for "Display and analysis of laboratory data" (6), RD 9.

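### From cycle 4, weekly sampling in arm A against once per cycle in arm B biases the worst-grade laboratory comparison, in expectation, towards arm A toxicity when abnormalities are short-lived

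*Protocol*

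**What the plan says.** **Visits.** The phase II flow chart (until protocol version 10) gives both arms four visits and four safety laboratory draws per 28-day cycle in cycles 1-3. From cycle 4, Protocol 6.1.2 states that arm B "will only be required to attend for one visit per cycle on day 1", plus imaging visits. The flow chart footnote says the same of arm B and of arm A patients who have stopped BI 836845: they "will only be required to visit on day 1 of each cycle". Telephone contact with arm B on days 8, 15 and 22 is optional. It covers AEs and concomitant medication, not blood samples.

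**Arm A on BI 836845.** Protocol 4.1.4.2 gives the infusion "with repeated weekly administration on day 1, 8, 15 and 22 of every 28 day cycle". Protocol 6.2.2 adds: "Safety assessments (safety laboratory tests and vital signs) must be performed prior to dosing on the infusion days in both phase Ib and phase II".

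**Analysis.** Protocol 7.3: "The safety profile for the phase II patients will be compared in a descriptive manner" between the two arms. SAP 7.8.2.1 lists "Worst CTCAE grade experienced during the on-treatment phase" among its outputs, with CTCAE transitions from baseline to worst, worst to last, and baseline to last value. SAP 7.8.1 counts patients with at least one AE. The readable SAP text has no table restricted to common draws, no exposure-adjusted rate and no mention of the unequal schedule.

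**The concern.** The worst of a set of values cannot fall, and usually rises, as draws are added. A patient treated for six cycles has 6 × 4 = 24 scheduled draws in arm A and 3 × 4 + 3 × 1 = 15 in arm B. A grade 3 value that appears and resolves between two day-1 visits is seen in arm A and missed in arm B. The worst-grade comparison therefore mixes drug effect with sampling frequency.

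AE counts may be affected by two routes. Weekly contact prompts more reports of minor events, and Protocol 5.2.2.2 has clinically relevant laboratory changes recorded as AEs.

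Safety of the combination against enzalutamide alone is part of the phase II objective in Protocol 7.1. Phase II is also meant to inform later development, so a difference created by the schedule could be read as toxicity of BI 836845.

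**Working it through.** The documents give no figure for AE or laboratory ascertainment, so there is none to reproduce on this point. The sizing model does reproduce: exponential times with the medians of Protocol 7.6 return all eight durations in Table 7.6:3, including 22.5 months. The same model is used below.

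**Inputs from the documents.** Cycle length 28 days, so cycle 4 starts at day 84 (2.76 months). Forty patients per arm. Median PFS about 3 months in arm B and 4.3-4.6 in arm A.

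**Assumptions.** PFS time stands in for time on treatment. True risk is equal in both arms. Abnormalities start at 0.05 or 0.10 per patient-month and last D days. One is found only if a scheduled draw falls inside it. Arm A patients stay on BI 836845. Unscheduled, end-of-treatment (EOT) and follow-up draws are ignored. Follow-up is cut at 22.5 months.

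**Step 1: who reaches cycle 4.** Share = exp(−ln 2 × 2.76 / median). A 3-month median gives 0.53 (21 of 40); 4.3-4.6 months gives 0.64-0.66 (about 26 of 40).

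**Step 2: draws.** With a 3-month median in both arms, expected scheduled draws per patient are 19.2 in A and 11.8 in B, a ratio of 1.62. Of these, 9.1 in each arm come before cycle 4.

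**Step 3: why duration drives the result.** Between draws g days apart, the chance of catching an abnormality is min(D, g)/g. From cycle 4, g is 7 in arm A and 28 in arm B:
- D = 3: 3/7 = 43% v 3/28 = 11%
- D = 7: 100% v 25%
- D = 14: 100% v 50%
- D = 28: 100% v 100%

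**Step 4: patients with at least one detected abnormality** (A v B, 3-month median in both arms):

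| Duration | 0.05 per month | Ratio | 0.10 per month | Ratio | Chance A count exceeds B, 40 per arm, rate 0.10 |
|---|---|---|---|---|---|
| 3 days | 8.2% v 5.1% | 1.60 | 15.2% v 9.9% | 1.53 | 71% |
| 7 days | 17.3% v 11.4% | 1.51 | 29.4% v 21.1% | 1.39 | 77% |
| 14 days | 17.3% v 13.4% | 1.29 | 29.4% v 24.0% | 1.23 | 66% |
| 28 days | 17.3% v 16.7% | 1.04 | 29.4% v 28.5% | 1.03 | 49% |

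A simulation at 0.10 per month and 7 days gave 29.3% v 21.1%. With 4.6 months in both arms, the ratios are 1.26-1.84 up to 14 days and 1.03 at 28 days.

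**Step 5: shared end-of-study draws.** A simpler model takes an independent 1% chance per draw, P = 1 − 0.99^draws. At a 3-month median it gives 16.3% v 11.0% (ratio 1.48).
- One shared EOT draw: 1 − 0.837 × 0.99 = 17.1% v 1 − 0.890 × 0.99 = 11.9%, ratio 1.44.
- Two shared draws (EOT and follow-up): 1 − 0.837 × 0.9801 = 18.0% v 1 − 0.890 × 0.9801 = 12.8%, ratio 1.41.

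The follow-up visit is due 42 (+7) days after stopping and the on-treatment period ends at 42 days, so the second draw may not always count.

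**Step 6: unequal exposure.** With medians of 4.6 (A) and 3 months (B), rate 0.10 and 7 days, the shares are 39.1% v 21.1%, a gap of 18.0 points. If both arms were sampled weekly, 39.1 − 29.4 = 9.7 points would remain from longer treatment alone. On the common schedule the result is 26.0% v 21.1%, so 4.9 points remain.

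**The case against.** A reader might infer that the tables will show excess toxicity in arm A, always against it, and equally for AEs and laboratory values. The documents do not support that.

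- The schedules are identical through cycle 3, and under the planning medians only about half of arm B reaches cycle 4.
- The effect is a bias in expectation. With 40 per arm, arm A's count exceeds arm B's with probability 49-77% in the cases above.
- Event rates and durations are assumptions. For abnormalities lasting four weeks the effect almost disappears, and an independent risk at each draw overlooks that weekly values in one patient are likely to be correlated.
- Arm A patients who stop BI 836845 may move to day-1 visits, and shared EOT and follow-up draws dilute the difference.
- AEs are collected continuously from consent to the end of the residual effect period (Protocol 5.2.2.2). A day-1 visit can therefore record events from the previous four weeks, and telephone contact is allowed.
- The safety comparison is descriptive, with no test attached, and the baseline-to-last tables do not depend on a maximum.
- Parts of the SAP are not in the public copy, and it defers to a technical plan, company standards and a project safety plan that we have not seen.

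All of this stands, and it limits the size and certainty of the point. It does not remove the bias from the worst-grade and worst-value tables. Continuous AE collection cannot recover a laboratory change that nobody measured. The day-1-only laboratory schedule of protocol version 10 does not help either: it dates from September 2019, and amendment 7 was already acting on phase II results in February 2018.

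**Conclusion.** The point holds in a limited form. The schedules differ from cycle 4, and the between-arm worst-grade and worst-value shift tables are biased in expectation towards more laboratory toxicity in arm A when abnormalities are transient. With equal true risk and a 3-month median in both arms, the expected ratio is about 1.2-1.6 for durations up to two weeks and 1.03-1.04 at four weeks. For that exposure these are upper bounds, because they keep every arm A patient on weekly infusions and leave out the shared EOT and follow-up draws.

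For AEs, only the likely direction can be stated, and only for non-serious events; the documents give no basis for a size. A certain excess in arm A, or a quantified AE bias, would go beyond them.

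**What to change.** **SAP 7.8.2.1.** Add supplementary between-arm worst-grade and shift tables using only draws common to both schedules: weekly in cycles 1-3, day 1 from cycle 4, and EOT and follow-up draws that fall in the on-treatment period. Keep the all-draw tables as the description of each arm. Add exposure-adjusted rates, because the common schedule removes the sampling difference but not the effect of longer treatment in one arm (step 6).

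**SAP 7.8.1.** Show AE incidence with onset in cycles 1-3 (through day 84) beside the full on-treatment table. It should be supplementary: as the primary comparison it would drop late and cumulative toxicity. State in the SAP and the report that contact and sampling were unequal from cycle 4.

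**Cost.** A few extra tables. Arm A's draws outside the common schedule are left out of the comparative laboratory tables only. No visit or clinical procedure changes.
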